15.2. Treatment of Missing and Spurious Data

See general definitions in chapter 5.4.

⁶⁹ analysis_set_Ilivia_SAR = Yes

15.3. Exclusion of Particular Information

See general definitions in chapter 5.5.

15.4. Descriptive Analyses

See general definitions in chapter 5.1.

15.5. Hypotheses & Statistical Tests

There are no pre-defined statistical hypotheses.

16. Primary Endpoint 1 Ilivia: SADE-free Rate

16.1. Analysis set

CIP chapter 11.1. Statistical design, methods and analytical procedures

All endpoints are analysed per-protocol (PP), whereby the analysis sets are defined for each hypothesis separately.

CIP chapter 8.1 General considerations

Tab. 4: Required visit windows (1 month is defined as 30 days)

	Window	Days post-implant
3 months post-implant	± 30 days	61 to 121

All analyses are performed for a subset of the Ilivia analysis set. To avoid an over-estimation of the SADE-free rate, patients with premature study termination less or equal 60 days after implantation are excluded from the analysis set if no primary endpoint occurred.

16.2. Variables

CIP chapter 8.3.1.1 Group A: Ilivia family related SADE-free rate through 3 months

The parameter of interest " $Ilivia_{SADE\ free}$ " is the device related SADE-d free rate per patient, which will be calculated by $Ilivia_{SADE\ free} = [1 - \text{number of patients with one or more ICD related SADEs (SADE-d}_{Ilivia}) \text{ until 3-month follow-up} \div \text{all patients in the analysis set}] * 100\%$. SADEs will be adjudicated by an internal adjudication board, whereby the seriousness and device relatedness will be re-examined. If any amply documented external physical influence (e.g. accident, sport, twiddling) or medical AE caused the SADE, it does not contribute to this endpoint. SADEs that occur later than the 3-months follow-up do not contribute to this endpoint.

In patients without 3 month FU, and in patients with a date of the 3-month Follow-Up outside the required visit window from 61 to 121 days post-implant, all SADEs until and including 121 days after implantation can contribute to the endpoint (if they fulfil the requirements for an endpoint).

Data file, list of AE evaluations, identifier parent_record_ID	Descriptive	Variable name	Variable label	Variable level	Nominal values
ae_evaluation_form_1	No	endpoint_ilivia → endpoint_ilivia1	relevant for the primary endpoint (Ilivia family related SADE-free rate)	nominal	Yes / No
ae_evaluation_form_1	No	AESTDT	Onset date	date	n.a.
ae_evaluation_form_2	No	endpoint_ilivia → endpoint_ilivia2	relevant for the primary endpoint (Ilivia family related SADE-free rate)	nominal	Yes / No
ae_evaluation_form_2	No	AESTDT	Onset date	date	n.a.

There are two evaluation CRFs. An AE is defined as endpoint relevant when both evaluations came to this result. All divergent evaluations have to be reported⁷⁰.

Data file, identifier patient_display_id_full	Descriptive	Variable name	Variable label	Variable level	Nominal values
implantation_general_data	No	imp_visdate	Date of implantation	date	n.a.
data_SAR	No	enddate_Ilivia_SAR	Date of Ilivia study termination	date	n.a.
data_SAR	No	date_1stIliviaSADE_SAR ⁷¹	Date of 1 st primary Ilivia-related SADE	dummy	No
data_SAR	No	Ilivia_primEP_analysis_set_SAR ⁷²	Analysis set Ilivia primary endpoint	nominal	Yes /No
data_SAR	Yes	Ilivia_primEP_SAR ⁷³	Ilivia-related SADE(s)	nominal	Yes /No

⁷⁰ Report any endpoint_ilivia1 ≠ endpoint_ilivia2

⁷¹ date_1stIliviaSADE_SAR = minimum AESTDT with
endpoint_ilivia1 = Yes AND
endpoint_ilivia2 = Yes
per patient_display_id_full

⁷² IF analysis_set_Ilivia_SAR = Yes AND
date_1stIliviaSADE_SAR - imp_visdate ≤ 60days OR enddate_Ilivia_SAR - imp_visdate ≥ 61 days
THEN Ilivia_primEP_analysis_set_SAR = Yes
ELSE Ilivia_primEP_analysis_set_SAR = No

⁷³ IF analysis_set_Ilivia_SAR = Yes AND
date_1stIliviaSADE_SAR ≠ missing AND
{[fu3_visdate ≠ missing AND fu3_visdate is compliant AND date_1st_IliviaSADE_SAR ≤ fu3_visdate] OR
[fu3_visdate ≠ missing AND fu3_visdate is not compliant
AND date_1st_IliviaSADE_SAR - imp_visdate ≤ 121 days] OR
[fu3_visdate = missing AND date_1stIliviaSADE_SAR - imp_visdate ≤ 121days] }
THEN Ilivia_primEP_SAR = Yes
ELSE Ilivia_primEP_SAR = No

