8.3 Endpoints and hypotheses

8.3.1 Primary endpoints and hypotheses

The global primary hypothesis consists of two primary hypotheses related to the SADE-free rate in group A and SADE-free rate related in group B, respectively. The global primary alternative hypothesis is accepted when the primary alternative hypothesis for group A or the primary alternative hypothesis related to group B, or both can be accepted.

8.3.1.1 **Group A:** Ilivia family related SADE-free rate through 3 months

The safety of the Ilivia ICD family will be evaluated by asking the investigator to record any adverse event. While all adverse events have to be recorded throughout the study, only the Serious Adverse Device Effects (SADE) possibly or securely related to the Ilivia ICD family devices (SADE-d_{Ilivia}) until 3-month follow-up are counted for this primary endpoint. Securely procedure related Serious Adverse Device Effects (SADE-p_{Ilivia}) are not counted. Further definitions are given in section 18.11. The primary hypothesis evaluates the SADE-d_{Ilivia} free rate (Ilivia_{SADE_free}). It is expected, that the rate will be significantly above 90%, the corresponding hypotheses definitions are:

Null hypothesis: $H_{0_Ilivia} : Ilivia_{SADE_free} \leq 90\%$

Alternative hypothesis: $H_{A_Ilivia} : Ilivia_{SADE_free} > 90\%$

The parameter of interest "Ilivia_{SADE_free}" is the device related SADE-d free rate per patient, which will be calculated by

$$Ilivia_{SADE_free} = [1 - \text{number of patients with one or more ICD related SADEs (SADE-d}_{Ilivia}\text{) until 3-month follow-up divided by all patients in the analysis set}] * 100\%.$$

SADEs will be adjudicated by an internal adjudication board, whereby the seriousness and device relatedness will be re-examined. If any amply documented external physical influence (e.g. accident, sport, twiddling) or medical AE caused the SADE, it does not contribute to this endpoint. SADEs that occur later than the 3-months follow-up do not contribute to this endpoint.

8.3.1.2 **Group B:** Plexa related SADE-free rate through 3 months

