18.2.1 Causality assessment

The relationship between the use of the investigational device (including the medical-surgical procedure) and the occurrence of each adverse event shall be assessed and categorized, considering the presence of confounding factors, such as concomitant medication/treatment, the natural history of the underlying disease, other concurrent illness or risk factors. Each SAE will be classified according to five different levels of causality. Based on MEDDEV 2.7/3 rev 3, the investigator will use the following categories to assess the relationship of the serious adverse event to the investigational medical device or procedures and the sponsor will review the investigator's categorization:

Not related: the relationship to the device or procedures can be excluded

Unlikely: the relationship with the use of the device seems not relevant and/or the event can be reasonably explained by another cause, but additional information may be obtained.

Possible: the relationship with the use of the investigational device is weak but cannot be ruled out completely. Alternative causes are also possible (e.g. an underlying or concurrent illness/ clinical condition or/and an effect of another device, drug or treatment). Cases where relatedness cannot be assessed or no information has been obtained should also be classified as possible.

Probable: the relationship with the use of the investigational device seems relevant and/or the event cannot reasonably be explained by another cause, but additional information may be obtained.

Causal relationship: Causal relationship: the serious event is associated with the investigational device or with procedures beyond reasonable doubt.

The investigators will distinguish between the serious adverse events related to the investigational device and those related to the device procedures (i.e. procedure related to the application of the investigational medical device only and therefore not to any other procedure for other devices or treatments applied later throughout the clinical investigation, for instance to treat adverse events). Replacement procedures of the investigational device are considered as an application of a new investigational device and shall be assessed accordingly. The sponsor will review the investigator's assessment of device or procedure relatedness.

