18.11 Definition of endpoint-related SADEs

The SADE-free rate calculated for primary endpoint 1 of the Ilivia family and primary endpoint 2 for the Plexa ICD lead will be based on the total number of subjects with at least one SADE related to the respective device.

Endpoint-related SADEs are complications, which are device-related adverse events that are corrected using invasive measures or require invasive measures to correct or which result in the loss of significant device function (e.g. lead dislodgement). Device-related adverse events, which are corrected by non-invasive measures (e.g. reprogramming) are considered observations and will not contribute to the primary endpoints.

Only SADEs directly related to the device in question (SADE-d) will be included in the endpoint. SADEs which are securely related to the implantation procedure (SADE-p) (e.g. pocket infection, etc.) will not be considered for the primary endpoints. Furthermore lead infections

will not be considered for the endpoint as long as the specific event cannot be securely classified as related to the investigational device. Inappropriate ICD therapies which are not related to a device defect (e.g. correct sensing and behavior of the device according to device specification) will also not be considered for primary endpoint analysis. Furthermore twiddler`s syndrome will not be considered for the endpoint analysis.

All serious adverse device effects that meet these primary endpoint criteria for the respective device will be included in the primary endpoint event analysis, respectively. Adverse events with a device relation of "not related" will not contribute to or be included in the evaluation of the primary safety endpoints of both devices.

The SADEs will be adjudicated by an internal adjudication board, whereby the seriousness and device relatedness will be re-examined.

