16.3. Treatment of Missing and Spurious Data

To avoid an over-estimation of the SADE-free rate, patients with premature study termination less or equal 60 days after implantation and without any primary endpoint are excluded from the analysis set.

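### A safety event on which the two evaluation forms disagree is never counted as a primary endpoint, and no consensus step or sensitivity test is pre-specified

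*SAP*

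**What the plan says.** Protocol 8.3.1.1 and 8.3.1.2 define the primary endpoints as SADE-free rates and provide for adjudication: "SADEs will be adjudicated by an internal adjudication board, whereby the seriousness and device relatedness will be re-examined". Protocol 18.11 repeats this. None of these sections says how a disagreement is settled.

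SAP 16.2 (Ilivia) introduces two evaluation forms and states: "An AE is defined as endpoint relevant when both evaluations came to this result". It adds: "All divergent evaluations have to be reported". SAP 23.2 has the same rule for Plexa.

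The footnotes put this into code:

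- Footnotes 70 and 97 list events on which the forms differ.
- Footnotes 71 and 98 take the first event date only from events marked Yes on both forms.
- Footnotes 72 and 99 use that date to decide whether a patient terminated by day 60 stays in the analysis set.
- Footnotes 73 and 100 set the endpoint to No when the date is missing.

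**The concern.** Each primary analysis is a single-arm safety test against a fixed 90% goal, and only a handful of events is allowed. The rule settles every disagreement the same way, towards passing. A patient whose only candidate event is disputed is scored event-free, or leaves the set if terminated by day 60. (A patient with another event marked Yes on both forms inside the window still counts.)

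Nothing else in the plan tests what the disputes do to the result. The alternative analysis in SAP 16.7 and 23.7 is a Kaplan-Meier estimate at 91 days; it addresses timing and censoring and states no different event definition. The documents do not say who completes the two forms, whether the readings are independent, or how the board closes a split. Under Protocol 11.5 either group alone can pass the investigation, so one changed verdict could decide the whole study.

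**Working it through.** **Inputs.** Null SADE-free rate 90% (Protocol 8.3.1); one-sided level 1.25% (Protocol 11.3, SAP 16.6 and 23.6); evaluable n of 94 and 166, enrolled 105 and 185, planned SADE-free rates 98% and 97% (Protocol 11.2).

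**The plan's own figures.** The p-value for x events in n patients is P(X ≤ x) with X ~ Bin(n, 0.10).

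| Group | Passes | Fails |
|---|---|---|
| A, n=94 | 3 events, p=0.01246 | 4 events, p=0.0357 |
| B, n=166 | 8 events, p=0.01215 | 9 events, p=0.0260 |

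These limits match the termination counts of 4 and 9 in Protocol 11.7. Power is 88.0% and 93.6%, so the stated sample sizes reproduce.

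**Direction.** For any given pair of forms, the both-Yes count cannot exceed the count under any other way of combining them. The direction is certain; the size is not.

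**When one disputed patient matters.**

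- Retained in the set: only if the agreed count is exactly at the limit. P(X=3 | n=94, 2%) = 0.171 and P(X=8 | n=166, 3%) = 0.064.
- Excluded by day 60, at the planned n: no verdict changes. In A, 3/93 (p=0.0135) and 4/94 both fail, while 2/93 (p=0.0036) and 3/94 both pass. In B, 8/165 (p=0.0129) and 9/166 both fail, while 7/165 (p=0.0054) and 8/166 both pass.

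**Error at a true 90% rate (assumption only).** Let each evaluator independently detect a true endpoint with probability s and make no false calls. A true event is then marked Yes twice with probability s² and is disputed with probability 2s(1−s). At s = 0.95 the counted event rate is 0.10 × 0.9025 = 0.09025, and the disputed rate is 0.10 × 2 × 0.95 × 0.05 = 0.0095.

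- All disputed patients retained: P(X ≤ 3 | 94, 0.09025) = 2.5% in A and P(X ≤ 8 | 166, 0.09025) = 3.2% in B. For s from 0.98 down to 0.90 the ranges are 1.7–4.8% and 1.8–7.2%.
- All disputed patients excluded: averaging over the number removed, with event rate 0.09025/0.9905 = 0.0911 in the rest and the limit recomputed for each reduced n, gives about 1.4% (A) and 1.8% (B).
- Group A at n=105, retained: the limit is still 3, so P(X ≤ 3 | 105, 0.09025) = 1.2%. That is below the nominal 1.25%, but compares with 0.53% when there are no disputes.
- Group B at n=185, retained: the limit is 9, so P(X ≤ 9 | 185, 0.09025) = 2.5%, against 0.88% without disputes.
- Over-calls only, each form wrongly Yes with probability f: the event rate is 0.10 + 0.90f². For f of 1% to 5% the error is 1.24–1.05% (A) and 1.20–0.96% (B), so nothing is inflated.

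**Would either-Yes be a better primary rule?** Assume s = 0.95 and f = 0.01 at the planned rates. The either-Yes event rate is 0.02 × 0.9975 + 0.98 × 0.0199 = 0.0395 in A and 0.03 × 0.9975 + 0.97 × 0.0199 = 0.0492 in B. Power is then 49% and 57%, against 91% and 96% under both-Yes.

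**The case against.** The strongest defence has four parts.

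1. The rule is fixed in advance and disputes must be reported. A reader can add the disputed patients to the count and see whether 3 becomes 4 or 8 becomes 9. This limits the harm, but the recount is left to the reader, and it must also allow for early-terminated patients re-entering the set.
2. Reconciliation is possible. Footnote 1 in SAP 5.7 lets data change through queries before closure, and SAP 5.4 allows analyses with and without unclarified spurious data where appropriate. The sponsor's procedures, which are not among these documents, may also describe the board's work. True, but neither SAP provision requires anything for divergent evaluations.
3. Requiring agreement guards against false calls. The power figures bear this out, and both-Yes is a defensible primary rule.
4. The larger error figures need every disputed patient retained and exactly the planned n. Retention is doubtful in group B, where repositioning, replacement or explantation of the lead is a mandatory drop-out (Protocol 8.8.4.1). This stands, and is why the excluded-patient figures are given alongside.

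A reader might also infer that the plan contradicts itself. SAP 16.3 says "To avoid an over-estimation of the SADE-free rate, patients with premature study termination less or equal 60 days after implantation" are removed if they have no endpoint, but that wording concerns short follow-up, not evaluator agreement. Protocol 18.2.1 says "Cases where relatedness cannot be assessed or no information has been obtained should also be classified as possible", and Protocol 8.3.1.1 counts "only the Serious Adverse Device Effects (SADE) possibly or securely related to the Ilivia ICD family devices". The first, however, guides the investigator when relatedness cannot be assessed. It does not cover two evaluators reaching opposite conclusions, nor the other endpoint criteria. Protocol 18.11 even resolves doubt the other way for lead infections, which "will not be considered for the endpoint as long as the specific event cannot be securely classified as related to the investigational device". The documents do not support a charge of contradiction.

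**Conclusion.** The point holds as a gap in a stated rule. Disputed events are always left out of the primary tests, this can only keep or raise the SADE-free rate relative to counting them, and no pre-specified step or test shows whether it matters. Severity is minor to moderate.

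The size cannot be fixed, because neither document gives a disagreement rate. At the planned n and rates, the chance of sitting at the limit where one retained disputed patient decides the verdict is 17% (A) and 6% (B). The error rates of 2.5% and 3.2% rest on independent evaluators, 95% sensitivity, no false calls and full retention. They fall to about 1.4% and 1.8% if disputed patients are excluded, and there is no inflation if there are no disputes or all are over-calls. A reader might infer that the 1.25% level is in fact doubled, or that either-Yes should replace the rule. The documents establish neither.

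**What to change.** In SAP 16.2 and 23.2:

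- Have the existing internal adjudication board settle each divergent evaluation by documented consensus before database closure, and state who completes the two forms and whether they do so independently.
- Derive footnotes 71–73 and 98–100 (event date, analysis set, endpoint flag) from that final decision.
- Pre-specify, as a sensitivity analysis, the exact binomial test and two-sided 97.5% confidence interval on the either-Yes count, with the analysis set re-derived under that rule so that patients terminated by day 60 are handled consistently.
- Keep consensus or both-Yes as the primary rule. No default of Yes for unresolved cases is needed, because the either-Yes test already bounds their effect.

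The cost is some SAP wording, one final-decision field per divergent event and one extra exact test per group. The downside is a little more adjudication and analysis work and a possibly slightly lower reported SADE-free rate.

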11.7 Termination criteria

Group A of the clinical investigation will be terminated after confirmed knowledge of at least 4 patients with one or more Ilivia-endpoint-related SAEs (see 18.11), because it would be impossible to accept the primary Alternative hypothesis 1 for the planned sample size.

Group B of the clinical investigation will be terminated after confirmed knowledge of at least 9 (or at least 10 in case of a low dropout rate) patients with one or more Plexa-endpoint-related SAEs (see 18.11), because it would be impossible to accept the primary Alternative hypothesis 2 for the planned sample size.

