23.1. Analysis set

All analyses are performed for the Plexa analysis set⁹⁶.

CIP chapter 11.1 Statistical design, methods and analytical procedures

All endpoints are analysed per-protocol (PP), whereby the analysis sets are defined for each hypothesis separately.

CIP chapter 8.1 General considerations

Tab. 4: Required visit windows (1 month is defined as 30 days)

	Window	Days post-implant
3 months post-implant	± 30 days	61 to 121

All analyses are performed for a subset of the Plexa analysis set. To avoid an over-estimation of the SADE-free rate, patients with premature study termination less or equal 60 days after implantation are excluded from the analysis set if no primary endpoint occurred.

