date_1stPlexaSADE_SAR - imp_visdate ≤ 60 days OR enddate_Plexa_SAR - imp_visdate ≥ 61 days
THEN Plexa_primEP_analysis_set_SAR = Yes
ELSE Plexa_primEP_analysis_set_SAR = No

¹⁰⁰ IF analysis_set_Plexa_SAR = Yes AND
date_1stPlexaSADE_SAR ≠ missing AND
{ [fu3_visdate ≠ missing AND fu3_visdate is compliant AND date_1stPlexa_SADE_SAR ≤ fu3_visdate] OR
[fu3_visdate ≠ missing AND fu3_visdate is not compliant
AND date_1stPlexaSADE_SAR - imp_visdate ≤ 121 days] OR
[fu3_visdate = missing AND date_1stPlexaSADE_SAR - imp_visdate ≤ 121 days] }
THEN Plexa_primEP_SAR = Yes
ELSE Plexa_primEP_SAR = No

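### The coded rules for both primary-endpoint analysis sets (SAP footnotes 72 and 99) lack brackets and a missing-value test, and so do not produce the sets the SAP describes

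*SAP*

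**What the plan says.** **Prose.** SAP 16.1: "All analyses are performed for a subset of the Ilivia analysis set". SAP 16.3 adds that "patients with premature study termination less or equal 60 days after implantation and without any primary endpoint are excluded from the analysis set", with the stated aim of not over-estimating the SADE-free rate. SAP 23.3 repeats this rule for Plexa. SAP 23.1 names two different sets: it opens with "All analyses are performed for the Plexa analysis set" and later has "All analyses are performed for a subset of the Plexa analysis set".

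**Code.** Footnote 72 (SAP 16.2) requires membership of the Ilivia analysis set, then AND, then on the next line "date_1stIliviaSADE_SAR - imp_visdate ≤ 60days OR enddate_Ilivia_SAR - imp_visdate ≥ 61 days". Footnote 99 (SAP 23.2) has the same form with "date_1stPlexaSADE_SAR - imp_visdate ≤ 60 days OR enddate_Plexa_SAR - imp_visdate ≥ 61 days". Neither groups the two OR terms, and neither tests whether the SADE date is present. Footnotes 73 and 100, which code the endpoint itself, do both.

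**Linked rules.** Footnotes 2 and 3 (SAP 6.3) set each device's end date to the overall termination date unless that group was ended earlier, with no restriction to members of the group. SAP 5.8 gives SAS as its example of software.

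**Stopping limits.** Protocol 11.7: "Group A of the clinical investigation will be terminated after confirmed knowledge of at least 4 patients" with endpoint events. For Group B the count is "at least 9 (or at least 10 in case of a low dropout rate) patients".

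**The concern.** These two variables are the denominators of both confirmatory tests.

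- **Brackets.** With AND evaluated before OR, the day-61 condition admits a patient by itself. A group-B-only patient, or one who failed eligibility, has an Ilivia end date by default and so enters the Ilivia primary set. Footnote 73 requires set membership before it records an event, so this patient can only be coded event-free. The same holds for Plexa through footnotes 3, 99 and 100.
- **Missing value.** Event-free patients have no SADE date. Where missing values sort below every number, the day-60 comparison is true for all of them, and the event-free early terminators whom the prose removes are kept. For Plexa, with brackets supplied, this returns the whole Plexa analysis set. The opening sentence of 23.1 names that same set, so a validator could take the faulty result as confirmed.

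Both errors run in one direction. They enlarge the denominator, raise the displayed SADE-free rate and shift the confidence interval upward.

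**Working it through.** **1. The plan's own figures.** Exact binomial test of an event rate of 10%, one-sided 1.25% (SAP 16.6, 23.6). The limit is the largest x with P(X ≤ x | n, 0.10) ≤ 0.0125.

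- Ilivia, n = 94: P(X ≤ 3) = 0.0125 (0.01246 unrounded) and P(X ≤ 4) = 0.036, so the limit is 3. Power at a 98% SADE-free rate is 0.880.
- Plexa, n = 166: P(X ≤ 8) = 0.012 and P(X ≤ 9) = 0.026, so the limit is 8. Power at 97% is 0.936.

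These agree with Protocol 11.2 and with the stopping counts of 4 and 9 in 11.7.

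**2. Logic.** S = in the device's analysis set; D = days from implant to first endpoint SADE; E = days from implant to end date. As written: S AND D ≤ 60 OR E ≥ 61.

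| S | D | E | Prose | As written, missing = false | As written, missing sorts low |
|---|---|---|---|---|---|
| yes | none | 180 | in | in | in |
| yes | 30 | 40 | in | in | in |
| yes | none | 40 | out | out | **in** |
| no | none | 180 | out | **in** | **in** |
| no | none | 40 | out | out | out |

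**3. Bracket fault alone.** The documents do not give the overlap O between groups, so it is assumed. Also assumed: 94 and 166 properly analysable patients, and 90% of other-group patients reaching day 61.

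- Ilivia n′ = 94 + 0.9 × (185 − O)
- Plexa n′ = 166 + 0.9 × (105 − O)

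O = 105 (every Ilivia patient also in group B): Ilivia 94 + 0.9 × 80 = 166, and Plexa stays at 166. If 80% to 100% reach day 61, Ilivia n′ is 158 to 174.

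O = 80: Ilivia 94 + 94 = 188 and Plexa 166 + 22 = 188 (94.5 and 22.5 rounded down).

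SADE-free rates with Clopper-Pearson two-sided 97.5% intervals:

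| Events | n | Rate (CI) |
|---|---|---|
| Ilivia 3 | 94 | 96.8% (90.0–99.5) |
| Ilivia 3 | 158 | 98.1% (94.0–99.7) |
| Ilivia 3 | 166 | 98.2% (94.3–99.7) |
| Ilivia 3 | 174 | 98.3% (94.5–99.7) |
| Ilivia 0 | 94 | lower limit 95.4% |
| Ilivia 0 | 166 | lower limit 97.4% |
| Plexa 8 | 166 | 95.2% (90.0–98.2) |
| Plexa 8 | 188 | 95.7% (91.2–98.4) |

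At Ilivia n = 166 the nominal pass limit rises from 3 to 8 events, which contradicts Protocol 11.7. If 94 real patients had a true 10% event rate, P(X ≤ 8 | 94, 0.10) = 39%. That would be the type I error only if 11.7 did not operate. While it operates, at most 3 events can be present and the error stays at 1.2%.

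**4. Missing-value fault alone (brackets supplied).** At most the planned drop-outs return, so n ≤ 105 and n ≤ 185.

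- Ilivia: the limit stays at 3 for every n from 94 to 105. Three events read at most 97.1% (91.0–99.5).
- Plexa: the limit is 8 for n = 166 to 179 and 9 from n = 180, which needs 180 − 166 = 14 event-free terminators by day 60. Type I error would then go from 1.2% to 2.6%. Eight events read at most 95.7% (91.0–98.3).

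**5. Both faults together, O = 105.** Ilivia n is at most 105 + 72 = 177. The limit is 8, and three events read 98.3% (94.6–99.7), close to the bracket fault alone.

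**The case against.** The footnotes are pseudo-code. Several others could not run as written, and two medication footnotes (22 and 91) mix AND and OR without brackets. The SAP states no operator precedence, and the line break in footnote 72 puts both OR terms together, which suggests the intended grouping. The prose says who is excluded. SAS is only an example, and in ordinary reading an absent date does not satisfy a day-60 limit. Sections 24.1 and 25.1 also name the parent set first and then narrow it. The overlap is unknown, and full overlap is unlikely to be exact because upgrade and exchange patients may join group A only. Protocol 11.7 caps the events. SAP 8.2 reports the parent-set sizes, the Kaplan-Meier analyses (16.7, 23.7) use those sets, and SAP 7.2 promises a list of early drop-outs.

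Much of this stands as a limit on the harm. The intent is recoverable, the sizes in step 3 are scenarios, and a primary denominator larger than its parent set should be noticed. It does not remove the defect. The SAP's other set and endpoint rules (footnotes 5, 6, 73, 74, 100) do bracket mixed conditions, and the medication footnotes define no confirmatory denominator. The missing-value fault stays inside the parent set, so the reported counts alone would not show it, although the drop-out list would allow a check by hand.

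**Conclusion.** The concern holds. Followed literally, footnotes 72 and 99 give analysis sets that contradict SAP 16.1/16.3 and 23.1/23.3. The bracket fault is the larger: under the assumed full overlap it raises the displayed Ilivia rate at three events by 1.4 percentage points (98.2 − 96.8) and the lower confidence limit by 4.3 points (94.3 − 90.0). The missing-value fault depends on the software and is small: it leaves the Ilivia limit unchanged and moves the Plexa limit only with at least 14 event-free early terminators, to a value 11.7 already foresees for low drop-out. While 11.7 operates, a false pass is unlikely, and the main harm is to the reported rates and intervals. This should be fixed as a code correction; it is not a design flaw, and the sample sizes are unaffected.

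**What to change.** In the notation of step 2, rewrite footnote 72 as S AND [ (D not missing AND D ≤ 60) OR E ≥ 61 ], using the Ilivia variables, and footnote 99 likewise with the Plexa variables. This reproduces the prose except for an endpoint dated after day 60 in a patient terminated by day 60, which is an edge case because adverse event reporting ends at termination (Protocol 8.5.15). Delete the opening sentence of SAP 23.1 so that only the subset remains. The end-date variables need no change.

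The cost is two footnotes, one deleted sentence and the matching program code, with no effect on design, data collection or sample size.
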